**D. Description, Risks and Justification of Procedures and Data Collection Tools:**

**Enrollment and Screening:** Study subjects will be contacted an enrolled through [name] clinic. Initial contact will be made by phone prior to a clinic appointment to discuss initial interest of the patient. Further information and enrollment will take place at a clinic visit or time of the patients choosing. Enrollment will take place in a private room at [name] clinic. Initial baseline and demographic information will be gathered for enrolled patients at the time of enrollment. Safety labs (comprehensive metabolic panel and urine pregnancy test for women of childbearing potential) will be drawn or performed at [name] clinic and will coincide with a scheduled clinic visit closest to study protocol initiation. The comprehensive metabolic panel will be drawn to evaluate Child-Pugh score if there is no comprehensive metabolic panel within the medical record within 30 days of protocol initiation.

**Visit 1 and 4:** (~8 hours): On visits 1 and 4 the patients will undergo intensive PK sampling. Inclusion and exclusion criteria will be reviewed with the patient at each visit prior to initiation of the protocol. Subjects will be admitted to the CTRC in the morning and a "saline-lock" will be placed. The dalbavancin preparations will be prepared and managed by [name] or [name] who are both clinical pharmacists with training in sterile drug preparation. The dalbavancin 1500 mg will either be administered, by CTRC nursing staff, intravenously (as randomly assigned) or into the intraperitoneal space (as randomly assigned) using the patient's existing peritoneal dialysis catheter with the patients currently prescribed dialysate. Following the blood and peritoneal fluid collection at the second dialysis volume exchange, the subjects will be discharged and asked to return at a scheduled time on day 7. Patients will also be given a specimen collection up with instructions to collect approximately 30 ml of peritoneal dialysate following their evening nocturnal dwell. The collected dialysate will be returned to the investigators.

**Visit 2, 3, 5, and 6:** (~60 minutes): A "saline-lock" will be placed and a single blood and peritoneal fluid sample will be collected at each of these visits. All blood and peritoneal fluid draws will be

completed at the outpatient CTTC. The patient will be discharged and follow up visits will be scheduled for day 14 or next intensive PK sampling visit.

**Washout:** During the 45 day or greater washout portion of this study the patients will not be asked to come in for any visits. This timeframe, which is greater than 5 half-lives of dalbavancin, is to ensure that all of the medication (dalbavancin) has left the patients' system before administering another dose of the medication.

**Laboratory tests:** The laboratory tests to be performed as part of this study include pregnancy testing to confirm eligibility and comprehensive metabolic panels if one is not documented within 30 days prior to the initiation of protocol to determine Child-Pugh score. These will be done at an initial screening visit if required to coincide with clinic appointment before visit 1.

**Pharmacokinetic Assessments:** 4 mL of blood will be collected in a purple top (EDTA) tube and 4 mL of peritoneal fluid in a urine collection cup at pre-dose, and 1, 2, 3, 4, 6, dialysis volume exchange. Blood and peritoneal fluid will be placed in an ice bath to chill until centrifuged. Plasma will be harvested within 30 minutes of each blood sample and will be stored at -80°C until assaying.

**Sample Coding and Storage:** Study samples will be coded with an indirect identifier and stored in [name] access-controlled laboratory.

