### IV. Research Methods

#### A. Outcome Measure(s):

The primary endpoints for the study are to (1) determine dalbavancin plasma pharmacokinetics in peritoneal dialysis patients after intravenous and intraperitoneal administration and (2) determine dalbavancin peritoneal fluid pharmacokinetics in peritoneal dialysis patients after intravenous and intraperitoneal administration.

Secondary endpoint is to evaluate patients for any adverse effects potentially associated with intraperitoneal administration of dalbavancin.

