#### C. Study Design and Research Methods

This study is an open label, cross-over study, evaluating the plasma and peritoneal fluid pharmacokinetics of dalbavancin after either intravenous or intraperitoneal administration. The

patients will be randomly assigned to receive dalbavancin either intravenously or intraperitoneally on study visit 1. The patients will receive the alternate administration technique following the washout period at visit 4. Patients will be administered dalbavancin either intravenously or intraperitoneally on study day 0. Pharmacokinetic analysis will be conducted on days 0, 7, and 14. Following the wash out period of 45 days or greater, the same 10 patients will cross-over and then be administered dalbavancin via the alternate administration technique received in visit 1 on study day 0. Pharmacokinetic analysis will be conducted again on days 0, 7, and 14. (see Appendix 1)

*Sample Size:*

Ten (n=10) patients will be evaluated in this pharmacokinetic evaluation. Since this is a descriptive pharmacokinetic study a sample size calculation was not performed

*Plasma and peritoneal fluid sampling:*

Dalbavancin will be administered on study day 0. On the intravenous administration day dalbavancin will be administered as a 30-minute IV infusion. On the intraperitoneal administration day, dalbavancin will be administered in the peritoneal dialysis fluid with a 6 hour dwell time. On day 0, patients will undergo plasma and peritoneal fluid pharmacokinetic sampling for determination of dalbavancin concentrations at time zero, 1 hour, 2 hours, 3 hours, 4 hours, 6 hours, at time of volume exchange. Patients will be given a specimen collection cup and asked to collect ~30 ml of peritoneal dialysate following scheduled nocturnal dwell approximately 24 hours following the administration of dalbavancin administration. Patients will report for a single PK measurement on study days 7 and 14. (18 total plasma and 18 total peritoneal fluid samples per patient). Blood samples will be drawn from a peripherally inserted intravenous catheter. Peritoneal fluid samples will be drawn from the already placed peritoneal dialysis catheter. Blood samples will be immediately centrifuged at 3000g and plasma and peritoneal fluid samples will be stored at -80°C until analysis.

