**Safety Assessments:**

All clinical and laboratory adverse events will be graded according to the Common Terminology Criteria for Adverse Events v4.0 as outlined in Appendix 3. All patient reported adverse events will be evaluated. The most common reactions seen with dalbavancin to date are nausea, vomiting, diarrhea, headache, rash, and pruritis. For patients on study protocol following both intravenous and intraperitoneal dalbavancin administration, in the event of grade 2 or higher clinical or laboratory adverse events, these will be reported to the study physician, [name] or the study safety officer [name] within 24 hours and the need for and type of follow-up care will be determined by [name] or [name] (e.g., physician evaluation, follow-up labs, discontinuation of study medication, etc). Subjects will be discontinued from study for any grade 3 or 4 adverse events associated with dalbavancin administration.

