Appendix 1:

Appendix 2. Schedule of Events

	Blood Volume (mL)	Tube Type	Visit 1	Visit 2	Visit 3	Washout	Visit 4	Visit 5	Visit 6
Duration (days)			1	1	1	At least 45	1	1	1
Consent			x						
CMP	7	Green	x				x		
Urine pregnancy test			x				x		
Study drug administration			x				x		
Intensive Pharmacokinetic Sampling (4 mL for each drug in purple top tubes)	36	Purple	x				x		
Follow up Pharmacokinetic Sampling	4	Purple		x	x				
Clinical Adverse Events Assessed			x	x	x		x	x	x
Blood volume (mLs) b			43	4	4		43	4	4

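### No adverse-event check is scheduled between discharge on day 0 and day 7, so events that start and resolve in that interval rest on recall of up to a week or on unprompted reports.

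*Combined protocol and SAP*

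**What the plan says.** Section IV.A states the safety objective broadly: "Secondary endpoint is to evaluate patients for any adverse effects potentially associated with intraperitoneal administration of dalbavancin". Aim 3 says the same.

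On the intraperitoneal dosing day, section IV.C says that "dalbavancin will be administered in the peritoneal dialysis fluid with a 6 hour dwell time". Section IV.D gives Visits 1 and 4 a length of about 8 hours and then states that "the subjects will be discharged and asked to return at a scheduled time on day 7". Section IV.C adds: "Patients will report for a single PK measurement on study days 7 and 14".

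The Appendix 2 row "Clinical Adverse Events Assessed" is marked at Visits 1 to 6 and nowhere else, which means days 0, 7 and 14 of each period.

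Between discharge and day 7 the only study activity is a dialysate sample that the patient takes at about 24 hours. Of this sample section IV.D says only: "The collected dialysate will be returned to the investigators". It does not say when or how, and it attaches no symptom question.

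Under Safety Assessments the plan says "All patient reported adverse events will be evaluated". It requires grade 2 or higher events to reach the study physician or safety officer within 24 hours. The text names no call, diary, questionnaire or recall window.

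**The concern.** The intraperitoneal route is the one whose safety the trial sets out to describe, and the endpoint covers any adverse effect, mild ones included. An event that begins after the patient goes home and has gone by day 7 can enter the data in two ways only: the patient remembers it at Visit 2 or 5, or reports it without being asked. Mild, short-lived events are the ones most easily lost.

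Two things are at stake. With 10 patients, a finding of no events after intraperitoneal dosing says less if capture is incomplete. Also, the 24-hour reporting rule starts only once somebody knows of the event, and for nearly a week after dosing that depends on the patient volunteering it.

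**Working it through.** The plan states no figure on this point, so there is none to reproduce. The check compares the schedule with the text and then illustrates the possible effect.

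**Length of the interval.** Inputs: a dosing visit of about 8 hours and a return on day 7 (section IV.D). Assume that dosing falls near the start of the visit and that the day 7 visit is at the same clock time.

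- Interval without a scheduled assessment: 7 × 24 − 8 = 160 hours, or 160 / 24 = 6.7 days.
- It is the same after both routes, because the schedule is the same in both periods.

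**What is observed directly.** The 6-hour dwell fits inside the visit of about 8 hours, and discharge follows the second dialysate exchange. Events that appear during the dwell, or that persist to day 7, can be seen at a scheduled assessment. The gap concerns events that begin after discharge and end before day 7.

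**Whether other data fill it.** Appendix 2 places the metabolic panel at Visits 1 and 4 only, and section IV.D describes it as a means of scoring Child-Pugh class. No laboratory test is scheduled on day 7 or 14.

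**Illustration of under-recording.** Inputs: n = 10 patients (section IV.C), each dosed once by each route. The true rate p of events in the gap and the share c that is captured are assumptions; the documents give neither. The chance of recording at least one event is 1 − (1 − p × c)^10.

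| Assumed rate p | Full capture (c = 1) | Half captured (c = 0.5) |
|---|---|---|
| 20% | 1 − 0.80^10 = 0.893 | 1 − 0.90^10 = 0.651 |
| 10% | 1 − 0.90^10 = 0.651 | 1 − 0.95^10 = 0.401 |
| 2% | 1 − 0.98^10 = 0.183 | 1 − 0.99^10 = 0.096 |

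At a 20% rate with 75% captured the figure is 1 − 0.85^10 = 0.803, so the loss is modest if recall is good.

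**Effect of calls at about 24 and 72 hours.** The longest stretch that a patient must recall becomes the largest of 24 − 8 = 16, 72 − 24 = 48 and 168 − 72 = 96 hours, in place of 160.

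**The case against.** The strongest reply is that the plan does ascertain these events. The day 7 assessment is not limited to symptoms present that day, so it can cover the whole week. A grade 2 event, as Appendix 3 describes it, calls for some intervention or limits daily activities, and is less likely to be forgotten than a grade 1 event. Patients may also have been told to call; the consent and contact pages are not available for this review, and neither is the content of Appendix 1. The proposed calls rely on recall too, only over shorter windows. All of this stands. It narrows the point to length of recall and absence of a prompt, and mainly to mild, self-limited events.

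A reader might go further and infer that peritoneal irritation is the harm the endpoint is meant to find, and that it would be expected in the hours to days after discharge. The documents support neither step. They do not name peritoneal irritation as the target or predict its timing, and the planned dwell is observed.

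A reader might also take the dialysate return as an existing early contact. Section IV.D does not fix its timing, so the sample could come back at the day 7 visit.

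Nor does 160 of the first 168 hours without contact measure events missed: two short calls would hardly alter that proportion, yet they would shorten recall.

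Finally, at low event rates the small sample limits detection more than capture does. At 2%, full capture gives only about an 18% chance of seeing one event. That is right, and it is why the probabilities above are illustrations only.

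**Conclusion.** The point holds in a limited form. Appendix 2 and section IV.D leave about 160 hours after each dose with no scheduled adverse-event assessment, and no prompted contact is written into that interval. The result is possible under-recording of mild transient events after either route, and a 24-hour reporting rule that, for this interval, waits on the patient. The size cannot be derived from the documents. Under the assumed rates of 2% to 20%, halving capture lowers the chance of recording at least one event by about 9 to 25 percentage points, and better recall lowers it by less. The illustration treats every event as falling in the gap and so overstates the loss for events seen at a visit.

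The primary pharmacokinetic aims are unaffected, and the documents do not contradict themselves here. This is an inexpensive improvement to the measurement of a stated secondary endpoint, not a flaw that undermines the trial.

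**What to change.** In section IV.D (Visits 1 and 4) and in the adverse-event row of Appendix 2, add a short structured adverse-event check by telephone in both periods, at about 24 hours and at about 72 hours after dosing. The first coincides with the patient's own dialysate collection and should take place whenever that sample is returned.

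Use the same questions after both routes (abdominal pain, cloudy effluent, fever, any other symptom), so that ascertainment does not differ by route. Grade the answers by CTCAE and pass grade 2 or higher events into the reporting rule already in the plan.

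Cost: 10 patients × 2 periods × 2 calls = 40 short calls by existing staff. There is no new visit, procedure or blood draw, and no change to sample size.

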### **II. Background and Significance:**

Every year in the United States approximately 110,000-115,000 patients are newly diagnosed with end-stage renal disease (ESRD) and begin treatment with renal replacement therapy. Nearly 10,000 of these patients are started on peritoneal dialysis (PD). The use of home dialysis has increased significantly (35% increase) in the last decade, with 95% of home dialysis patients undergoing PD. Infectious peritonitis is a leading major morbidity associated with PD, and it accounts for approximately 18% of infection-related mortality in PD patients. Severe or prolonged peritonitis can lead to peritoneal membrane failure, ultimately causing technical failure of PD and requiring transition to traditional hemodialysis methodologies. Rapid and effective treatment of peritonitis is required to reduce inflammation and preserve peritoneal membrane function. The current standard of care involves empiric antibiotics covering gram positive organisms as staphylococcus aureus, coagulase negative staphylococcus and enterococcus are common infecting pathogens. Vancomycin is commonly employed at most institutions as there is a risk of MRSA infections in this patient population. Addition of a second drug for gram negative bacteria coverage is recommended until culture and sensitivity results are available. Intravenous or intraperitoneal administration of antibiotics can be utilized; however, guidelines recommend the intraperitoneal administration of antibiotics with a dwell time of at least 6 hours because it provides instant, high, and sustained concentrations of the antibiotic in the peritoneal fluid. Although vancomycin covers the majority of gram positive organisms that cause peritonitis, its use can be cumbersome in PD patients. Plasma vancomycin drug concentration monitoring must occur to evaluate for vancomycin accumulation. Additionally, vancomycin must be re-administered every 3-5 days in order to maintain steady-state trough concentrations around 15 mcg/ml. Similarly to vancomycin, dalbavancin interferes with cell wall synthesis. This is done through binding of the D-alanyl-D-alanine terminus of the cell wall peptidoglycan. Dalbavancin has been shown to rapidly reach therapeutic systemic concentrations and to have an extended half-life of ~8.5 days. Dalbavancin has been shown safe and effective with a treatment doses of 1500 mg once or 1000 mg followed by a 500 mg dose on day 7. Dalbavancin pharmacokinetics were evaluated in patients who had hepatic or renal impairment. This study showed compared to healthy subjects dalbavancin exposure was not increased in mild renal impairment, exposure was ~50% higher in moderate renal impairment, 100% higher in severe renal impairment, and not significantly different in end stage renal disease

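### No safety contact is scheduled beyond day 14 after the second dose and no adverse-event reporting window is defined, so late events can be missed

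*Combined protocol and SAP*

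**What the plan says.** **Schedule.** The row "Clinical Adverse Events Assessed" in Appendix 2 is marked at visits 1 to 6. The washout column is blank in that row, and there is no column after visit 6. Section IV.C fixes the timing in the second period: "Pharmacokinetic analysis will be conducted again on days 0, 7, and 14". Visits 4, 5 and 6 are therefore days 0, 7 and 14 after the second dose. The visit descriptions in section IV.D mention no contact after visit 6.

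**Interval after the first dose.** The Washout paragraph of section IV.D states: "During the 45 day or greater washout portion of this study the patients will not be asked to come in for any visits". It justifies the length as follows: "This timeframe, which is greater than 5 half-lives of dalbavancin, is to ensure that all of the medication (dalbavancin) has left the patients' system". The Background (section II) describes dalbavancin as having been shown "to have an extended half-life of ~8.5 days".

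**Reporting rule.** Safety Assessments in section IV.D says "All patient reported adverse events will be evaluated" and gives no end date. The 24-hour reporting rule for events of grade 2 or higher is worded "For patients on study protocol following both intravenous and intraperitoneal dalbavancin administration". The protocol does not say when a patient ceases to be on study protocol.

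**Endpoint.** The third specific aim, and the only secondary endpoint in section IV.A, is adverse effects potentially associated with the intraperitoneal route.

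**The concern.** The two doses are the same size, and either may be the intraperitoneal one. After the first, the patient returns at visit 4, when by the protocol's own reasoning the drug has cleared. After the second, the last scheduled contact comes while a substantial part of the systemic drug is still present. An event that begins after day 14 of the second period reaches the study only if the patient volunteers it, and nothing tells patient or staff how long such reports are wanted.

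This bears on the one safety question the trial asks. Patients given the intraperitoneal dose second have 14 days of scheduled follow-up for the route named in the endpoint. With 10 patients, one late event recorded or lost would change the safety description.

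**Working it through.** **Inputs.** Half-life about 8.5 days (section II); washout at least 45 days, described as more than 5 half-lives (section IV.D); last assessment after the second dose on day 14 (section IV.C and Appendix 2); 10 patients (section IV.C).

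**1. The plan's own figure.** 5 × 8.5 = 42.5 days, and 45/8.5 = 5.29 half-lives. The statement that 45 days exceeds 5 half-lives reproduces.

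**2. Same scale for the second dose.** 14/8.5 = 1.65 half-lives at the last scheduled contact.

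**3. Fraction remaining,** assuming mono-exponential decline, 2^(−t/8.5):

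| Days after dose | Half-lives | Remaining |
|---|---|---|
| 14 | 1.65 | 31.9% |
| 42.5 | 5.00 | 3.1% |
| 45 | 5.29 | 2.5% |
| 59 | 6.94 | 0.8% |

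Half-life in peritoneal dialysis patients is something the study sets out to measure. If it lay between 7 and 12 days (an assumed range), the day-14 figure would run from 2^(−14/7) = 25% to 2^(−14/12) = 45%.

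These are fractions of systemically available drug. Section IV.C gives the intraperitoneal dose a 6-hour dwell, and section IV.F treats the fraction absorbed as a quantity to be estimated. For that route, 32% applies to the absorbed amount and not to the 1500 mg instilled.

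**4. Last scheduled look at each dose.**
- Second dose: day 14.
- First dose: day 14, then visit 4. Visit 4 is at least 45 days after the first dose if the washout is counted from dosing, or at least 14 + 45 = 59 days if it is counted from visit 3, where Appendix 2 places it.

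**5. Time without a scheduled contact.** Up to day 45, the second dose has 45 − 14 = 31 days with no contact and none at the end. Over 10 patients that is 10 × 31 = 310 patient-days. The first dose has the same gap, but a visit follows it.

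**The case against.** The strongest reply is that visit 4 is a dosing day, and its adverse-event mark may simply mirror the one at visit 1. On that reading the marked schedule is the same for both doses (days 0, 7 and 14), and nothing in the text makes visit 4 a look-back over the washout. This stands as a limit on the claim. A reader might infer that the first dose has a defined window of 45 days or more against 14 for the second, but the documents do not say so. They do place the patient in front of study staff at visit 4, with adverse events on the schedule. The second dose has no counterpart.

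Secondly, a reader might infer that collection stops at day 14. It is not stated. The rule on patient-reported events is open-ended, and participants come from a clinic that follows them anyway. Late events can be missed; the documents do not show that they will be. An open-ended rule still adds no contact, and routine clinic care is not protocol safety follow-up.

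Thirdly, a reader might infer a biased comparison of routes. Order is randomised and no comparison of event counts between routes is planned; the statistical comparisons in section IV.F are of pharmacokinetic and pharmacodynamic results. Even if visit 4 does look back 45 days, an even split of sequences gives each route the same mean window: (5 × 45 + 5 × 14)/10 = 29.5 days. The unequal follow-up belongs to period. It would fall on route only through an uneven split, and no allocation ratio or blocking is stated.

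Finally, the 45 days is offered as a condition for giving the next dose, not as a safety follow-up standard. That is correct. Using it as the follow-up length is a reviewer's judgement, chosen because it is the protocol's own figure for clearance.

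**Conclusion.** The point holds as a worthwhile, low-cost improvement. The last scheduled safety contact after the second dose is at 1.65 half-lives, with about 32% of systemically available drug remaining (25% to 45% for an assumed half-life of 7 to 12 days). The first dose is followed by a further visit after at least 5.29 half-lives. The reporting window is undefined, and so is the period that visit 4 covers. Late events after the second dose can therefore go unrecorded, including in every patient whose second dose is intraperitoneal.

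The percentages rest on mono-exponential decline at the cited half-life, while section IV.F allows for up to three compartments. The schedule gap does not depend on them.

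Two further inferences are not supported. One is that drug would persist longer because exposure is higher in severe renal impairment: the Background reports exposure in end-stage patients on dialysis as not significantly different from healthy subjects, and all participants are on chronic dialysis. The other is that particular listed reactions arise late: the risk section gives no time of onset for any of them.

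**What to change.** 1. Add to Appendix 2 one scripted adverse-event contact at least 45 days after the second dose, by telephone or at a routine dialysis clinic visit.
2. State that the visit 4 assessment is made before dosing and covers the interval since visit 3, with onset dates recorded so that events can be assigned to the first dose.
3. Define the adverse-event reporting window in Safety Assessments, the same for both doses.
4. Tabulate events by route over the same post-dose windows, days 0–14 and days 0–45.

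A contact partway through each interval, on the same post-dose day in both periods, would shorten recall but is optional.

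The cost is one call for each of 10 patients, a small amendment, and last-patient-out later by 45 − 14 = 31 days. No new procedure is needed, and dosing and the pharmacokinetic sampling are unchanged.

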##### *Pharmacokinetic analysis:*

Plasma and peritoneal fluid concentration-time data for dalbavancin will be evaluated using a multi-compartment model in Phoenix WinNonlin (Pharsight corporation). One, two, and three compartment models will be explored. The following PK parameters will be calculated for plasma and dialysate samples: Cmax – measured, Tmax – measured, Cmin – measured. Fraction of intraperitoneal (IP) dose absorbed [(Dose – drug concentration remaining in dialysate at end of

antibiotic dwell)/Dose].  $K_{el}$  – elimination rate constant.  $T_{1/2} = 0.693/K_{el}$ .  $K_{pc0-6}$  – rate constant for distribution of dalbavancin from peritoneal cavity between 0-6 hours. Distribution half-life in the peritoneal cavity between 0-6 hours ( $t_{1/2} = \ln 2/k_{pc0-6}$ ). Clearance systemic =  $(F \times \text{Dose})/AUC_{0-\infty}$ . Clearance peritoneal – dalbavancin concentration in spent dialysate/AUC of peritoneal fluid. Non-dialysis clearance –  $Cl = Cl_{plasma} - Cl_{peritoneal}$ .  $AUC_{0-\infty}$  – linear trapezoidal method.  $AUC_{0-12}$  hours – linear trapezoidal method. Volume of distribution for each compartment –  $Cl/k_{el}$ ; nonsteady state equations will be utilized. The ratio of plasma dalbavancin to dialysate plasma concentration at each time point –  $C_{plasma}/C_{dialysate}$  and via  $AUC_{plasma}/AUC_{dialysate}$ . Given the sample size of 10 patients completing each treatment modality we will be able to calculate means and standard deviations for all included pharmacokinetic parameters. We will incorporate the dalbavancin PK parameters into a nonlinear mixed effects model (NONMEM) or ADAPT II to determine the pharmacokinetics and examine the effects of varying dosing strategies on plasma and peritoneal fluid concentrations.

*Analysis of pharmacodynamic targets:*

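### In the intraperitoneal period no dialysate sample is taken at the start of the dwell, so measured dialysate Cmax is low, and so is AUC0-6 if the curve starts at the pre-dose value

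*Combined protocol and SAP*

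**What the plan says.** One sampling clock serves both routes. Section IV.C (Plasma and peritoneal fluid sampling) lists day-0 samples "at time zero, 1 hour, 2 hours, 3 hours, 4 hours, 6 hours, at time of volume exchange". Section IV.D (Pharmacokinetic Assessments) lists "peritoneal fluid in a urine collection cup at pre-dose, and 1, 2, 3, 4, 6, dialysis volume exchange". The first calls the opening sample time zero, the second pre-dose. Later fluid samples are a home collection, where patients "collect ~30 ml of peritoneal dialysate following scheduled nocturnal dwell approximately 24 hours" after dosing, and single samples on days 7 and 14. The stated total is "18 total plasma and 18 total peritoneal fluid samples per patient".

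On the IP day, "dalbavancin will be administered in the peritoneal dialysis fluid with a 6 hour dwell time". The nominal dose is 1500 mg by either route, given in the patient's own prescribed dialysate (Section IV.D, Visit 1 and 4). The protocol lists no sample just after instillation, no assay of the dosed bag, and no record of instilled or drained volume.

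Section IV.F (Pharmacokinetic analysis) defines Cmax as measured and computes AUC0-12 and AUC0-infinity by the linear trapezoidal method. It defines k_pc0-6 as the "rate constant for distribution of dalbavancin from peritoneal cavity between 0-6 hours", without an estimating formula. Fraction absorbed is the dose, less the drug concentration left at the end of the dwell, divided by the dose. One- to three-compartment models are also to be explored. No rule is given for the dialysate concentration at time 0 (C0) after IP dosing.

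**The concern.** After IV dosing a pre-dose zero is the natural left endpoint for peritoneal fluid, which starts without drug. After IP dosing the fluid starts at its highest concentration and falls. A pre-dose value is about zero: exactly so in a first period, and nearly so in a second, after a washout of at least 45 days (45/8.5 = 5.3 of the half-lives quoted in the Background). Joining it to the 1 h value draws a rising line where the true curve declines. A Cmax that must be measured cannot be earlier than 1 h.

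Peritoneal-fluid pharmacokinetics by route is Aim 2 and one of the two primary endpoints. Dialysate AUC also enters the plasma-to-dialysate AUC ratio and the denominator of peritoneal clearance. The error is systematic, so averaging over ten patients does not remove it. It touches only the dialysate profile of the IP period.

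**Working it through.** **1. The plan's sample count.** Fluid times per period, taking 6 h as the exchange: 0, 1, 2, 3, 4, 6, 24 h, day 7, day 14, which is 9. Two periods give 2 × 9 = 18, the stated figure. If 6 h and the exchange are separate samples, the total is 2 × 10 = 20. Neither count leaves room for a start-of-dwell sample. (Plasma, without the 24 h home collection, gives 16 or 18, so no single reading yields 18 for both fluids.)

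**2. AUC0-6 and Cmax in IP dialysate.** Assumption: first-order loss, C(t) = C0·exp(−kt), k = ln 2/half-life. The documents give no cavity half-life, so a range is shown. The percentages do not depend on fill volume.

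- Exact AUC0-6 = C0(1 − e^(−6k))/k.
- Planned: linear trapezoid on 0, 1, 2, 3, 4, 6 h with C(0) = 0.
- Starting at zero removes a triangle of 0.5 h × C0.

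For a 2 h half-life and C0 = 1, the values at 1, 2, 3, 4 and 6 h are 0.707, 0.500, 0.354, 0.250 and 0.125. The trapezoid is 0.354 + 0.604 + 0.427 + 0.302 + 0.375 = 2.061. The exact area is 0.875/0.3466 = 2.525. The ratio is 0.816, or −18.4%. With C(0) = 1 the trapezoid is 2.561, or +1.4%.

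| Half-life (h) | Lost in 6 h | AUC0-6 from pre-dose zero | AUC0-6 with true C0 | 1 h value vs C0 |
|---|---|---|---|---|
| 2 | 0.875 | −18.4% | +1.4% | −29% |
| 3 | 0.75 | −14.7% | +0.7% | −21% |
| 4 | 0.65 | −13.0% | +0.4% | −16% |
| 6 | 0.50 | −11.4% | +0.2% | −11% |
| 12 | 0.29 | −9.8% | +0.05% | −6% |

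A wider assumption, fraction absorbed in 6 h from 0.10 to 0.90, gives −8.8% to −19.6% for AUC0-6 and −1.7% to −31.9% for Cmax.

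**3. AUC0-12.** Assumptions: 2 L fill (1500/2 = 750 mg/L) and a constant level after the exchange. For 0.50 absorbed and 20 mg/L after the exchange:

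- True: 3246 + 6 × 20 = 3366 mg·h/L.
- Trapezoid from pre-dose zero with a post-exchange sample: 2877 + 120 = 2997, about −11%.
- Trapezoid run straight from 375 mg/L at 6 h to 20 mg/L at 24 h: the interpolated 12 h value is 375 − 355 × 6/18 = 257, and 2877 + 6 × (375 + 257)/2 is about 4772, or +42%.

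Over 0.10 to 0.90 absorbed and 5 to 50 mg/L after the exchange, the net error is about −8% to −19% with a post-exchange sample. Without one it runs from +69% to −11%, and is positive throughout for fractions up to 0.75.

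**4. k_pc0-6.** In this model the log-linear slope through 1, 2, 3, 4 and 6 h returns k exactly, using neither C0 nor dose. Only a two-point ln(C0/C6)/6 with nominal C0 depends on the dose. A 10% delivered-dose shortfall then adds −ln(0.9)/6 = 0.0176 per h, which is +15% when k = 0.1155 (0.50 absorbed).

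**5. Fraction absorbed.** If amounts are used and a share r of the nominal dose is delivered, a true F reads 1 − r(1 − F). With r = 0.9, 0.10 reads 0.19, 0.50 reads 0.55 and 0.90 reads 0.91. As written, the formula subtracts a concentration from a dose: at 2 L a true 0.10 reads (1500 − 675)/1500 = 0.55.

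**The case against.** The plan never says that the pre-dose value starts the IP dialysate curve. A nominal, back-extrapolated or model-based C0 would each repair AUC0-6 without a new sample, and compartment models are planned. AUC0-6 is not a listed parameter. The study is descriptive and its hypothesis concerns two weeks, so the 24 h, day 7 and day 14 samples matter more than the first hour. All of this stands, and it makes the AUC error conditional.

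A reader might go further and infer that every IP dialysate AUC is biased low, so that the route comparison is tilted against IP. The documents do not support that: step 3 shows that the sign for AUC0-12 turns on an unstated rule for the exchange. A reader might also infer that k_pc0-6 rests on an unverified dose. No formula is given, and the 1 to 6 h slope needs no dose. Nor does the plan say that F in systemic clearance is the dialysate fraction absorbed; in a crossover with an IV period it could be a plasma AUC ratio. Nothing in the documents shows that dose is lost in preparation.

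What the objection does not remove: a modelled C0 cannot change a Cmax defined as measured. A nominal C0 needs a fill volume that is not stated to be recorded. Back-extrapolation assumes that nothing faster happens in the unsampled hour. A sample missed at dosing cannot be taken later.

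**Conclusion.** The point holds in a limited form. With no fluid sample between instillation and 1 h, measured IP dialysate Cmax is low by about 6% to 29%. AUC0-6 is low by about 10% to 18% if the trapezoid starts at the pre-dose value. Both ranges assume first-order loss with half-lives of 12 h down to 2 h. The net direction for AUC0-12 or longer is open until the plan states how post-exchange fluid is handled. For k_pc0-6 only the first-hour phase is unobserved. Fraction absorbed rests on the nominal dose, so a delivery shortfall would read as absorption; subtracting a concentration from a dose is a separate fault in that formula and can be larger. This is an inexpensive improvement to a primary-endpoint compartment, not a flaw that undermines the study.

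**What to change.** For the IP period only, in Sections IV.C, IV.D and IV.F:

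- Add one 4 mL fluid sample from the catheter right after fill and mixing. Use it as the time-0 dialysate value for AUC and Cmax.
- Keep the pre-dose sample as a carryover check, and state that it is not the left endpoint of the IP dialysate curve.
- State how fluid after the exchange enters AUC0-12 and longer intervals, and how k_pc0-6 is estimated.
- Record drained volume and compute fraction absorbed from amounts.
- If delivered dose is to be verified, assay the mixed bag and record instilled volume. Do not use the bag value as the cavity C0: if residual fluid were 10% of the fill (an assumption), it would be 10% too high.
- Reconcile time zero with pre-dose, and update the sample count: 18 fluid samples become 19, or 20 become 21 if 6 h and the exchange are separate. A bag assay adds one more.

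The cost is one extra dialysate sample and assay per patient, ten in all, or two per patient if the bag is also assayed. No visit or blood draw is added.
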